We are writing to request an amendment to our approved study protocol to add an additional question to assess suicidality. If students are suicidal, we want to eliminate them from the study, provide access to resources for them, and alert student counseling services. We have attached 1. Our approved IRB protocol with a revised procedure on pg 8 of the protocol itself, indicating the suicidal risk assessment question, and the suicide risk assessment question itself on the bottom of page 18. 2. The sections we changed as individual documents so you do not need to search for the changes in the IRB protocol itself. We appreciate your time and effort in reviewing this amendment and are happy to provide any additional information or clarification as needed.

A handwritten signature in black ink, appearing to read "[name]".

[name]
Assistant Professor,
Department of Psychology
Prairie View A&M University

PROCEDURES

What will participants be asked to do? (Describe the study in detail from recruitment to completion)
If you need additional space, put "see attached" in the box below and attach complete description of procedures.

Participants will access the study via an online link provided by email or via word of mouth. They will first answer a question to assess their suicide risk. If they have not had suicidal thoughts in the previous three weeks, they will continue on to the study. If they indicate they have had such thoughts in the prior three weeks, they will be disqualified from the study and a screen will appear with contact information regarding mental health resources. [name] will then reach out to Student Counseling Services and ask them to reach out to the students to follow-up and provide additional support. For those students who continue with the study, they will take the PHQ-9 and the GAD-7 to measure their depression and anxiety levels. If they score 5 or above on either test they will be invited to participate in the therapy part of the study. In this part of the study the participant will be assigned to either receive individual teletherapy or group teletherapy for 12 weeks. This therapy takes place via text. Participants may be asked to read psychoeducational materials and complete homework assignments. Participants assigned to the individual therapy, will receive support in the form of direct asynchronous communication with the therapist. Participants assigned to the group therapy will receive support in the form of direct asynchronous communication with the therapist and asynchronous communication with peers struggling with similar issues. Throughout the at week 4, 8 and 12 of therapy, participants will take the GAD-7, PHQ-9, and self-report questionnaires to measure their engagement and experience.

Describe the location where research activities will take place:

The research will take place on participants personal electronic devices by logging on to the web-based TheraGroup platform. TheraGroup is a proprietary real-time virtual based platform that provides text based group therapy. It is a cloud software that offers HIPAA compliant asynchronous text chat.

How long will the participants be engaged in research? (length of time, i.e. 15 minutes on day 1, etc.):

up to 12 weeks

During data collection, describe what steps will be taken to ensure participant privacy:

Due to the longitudinal design of this project, collecting identifiable data is necessary. Specifically, participants' names and contact information are needed to match participant information at different time points and to contact participants about distributing their gift card compensation. In order to preserve participant confidentiality and minimize the potential harm of participant information being identified, participants' will be prompted to create an identification number comprised of the first two letters of their last name combined with the last four digits of their phone number (e.g., Jane

Is the research anonymous or confidential? (**Cannot be both**)

Anonymous: The identity of the participant cannot be readily determined by the investigator AND the identity of the participant is not connected to information gathered.

Confidential: Research participants can be identified; however, information gathered will be protected.

Provisions for anonymity/confidentiality:

Secure storage (**required**)

Replies coded

What specific steps will be followed to ensure anonymity or confidentiality of participants' responses?

The participant ID and identifying information (name-code-index) as described above will be stored on a password protected spreadsheet. Only [name] and her team will have the ability to de-identify participants. Disclosure of data via research dissemination methods such as presentations at conferences and in study related publications will not contain identifying information. In addition, for the group therapy, participants use a name they make up for the purpose of the group only to ensure they remain anonymous. The therapy contains no face to face modalities. It all occurs via text based communication.

Participants will access the study via an online link provided by email or via word of mouth. After providing basic demographic and their email address (to receive payment), they will then answer a question to assess their suicide risk. If they have not had suicidal thoughts in the previous three weeks, they will continue on to the study. If they indicate they have had such thoughts in the prior three weeks, they will be disqualified from the study and a screen will appear with contact information regarding mental health resources (see attached survey measures). [name] will then explain the situation to Student Counseling Services and provide the student's contact information (email address) to them. Student Counseling Services will then make contact with the student and carry out protocols they have in place to help suicidal students. For those students who continue with the study, they will take the PHQ-9 and the GAD-7 to measure their depression and anxiety levels. If they score 5 or above on either test they will be invited to participate in the therapy part of the study. In this part of the study the participant will be assigned to either receive individual teletherapy or group teletherapy for 12 weeks. This therapy takes place via text. Participants may be asked to read psychoeducational materials and complete homework assignments. Participants assigned to the individual therapy, will receive support in the form of direct asynchronous communication with the therapist. Participants assigned to the group therapy will receive support in the form of direct asynchronous communication with the therapist and asynchronous communication with peers struggling with similar issues. Throughout the at week 4, 8 and12 of therapy, participants will take the GAD-7, PHQ-9, and self-report questionnaires to measure their engagement and experience.

5. It was boring to use the telehealth therapy services
6. I felt frustrated using the telehealth therapy services
7. I found the telehealth services confusing
8. I felt unmotivated to use the telehealth services

User Feedback Experience

1. What, if anything, did you enjoy about your experience in using the guided telehealth therapy?
2. What, if anything, could be improved about your experience in using the guided telehealth therapy?
3. Did you feel the psychoeducational content was culturally relevant to you as a Black individual? Please explain

Suicide Assessment

“In the past few weeks, have you been thinking about killing yourself?”

If participant answers "yes" show the following resources:

- 24/7 National Suicide Prevention Lifeline [name] En Español:
[name]
- 24/7 Crisis Text Line: Text “HOME” to [name]
- PVAMU Student Counseling Services: [contact]
- 9-1-1

PRAIRIE VIEW A&M UNIVERSITY

A Member of the Texas A&M University System

To: **[name].**, Principal Investigator

From: **[name].**
IRB Chair

Date: October 28, 2024

Re: IRB Protocol #2024-044

The IRB protocol application submitted by you titled “Guided Group Telehealth to Deliver Evidence-Based Therapeutic Care to Black college students” has been deemed expedited and approved on October 28, 2024.

Any future correspondence regarding this study should reference the Protocol Title and Number. Please also make sure to use the consent forms with the “PVAMU Approved” Stamp.

A handwritten signature in black ink that reads "[name]".

[name].
IRB Chair
Office: [contact]

PLEASE NOTE: As the principal investigator of this study, you assume the following responsibilities:

- **Record Retention:** Records must be retained for at least 3 years after study completion.
- **Amendments:** Changes to research study activities may not be initiated without IRB approval.
- **Unanticipated Problems/Adverse events:** Any unanticipated problems/adverse events must be reported to the IRB immediately.
- **Informed Consent/Accent:** If applicable, all subjects must be given a copy of the stamped consent/assent document approved by the IRB (see attached).
- **Completion:** Once the study is complete, you must complete the [IRB-Completion-Report-Form.pdf \(pvamu.edu\)](#) and submit it to the Office of Research Compliance at [contact].

Prairie View A&M University
IRB Protocol Application

Received 7/8/2024

INSTRUCTIONS

1. Complete Training

PI, Co-Investigator and anyone interacting with potential participants must complete necessary training.

Refresher training must be completed every three years. More details can be found at: <http://www.pvamu.edu/research/office-of-research-compliance/207-revision-v1/irb-training/>

2. Complete Form

Form must be typed and free of typographical/grammatical errors.

3. Attach Documents to Application

- Recruitment materials as applicable: flyers, letters, scripts, e-mail, etc.
- Consent documentation as applicable: consent protocol, consent form or assent form
- Survey and/or Interview Questions

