Data will include the following: 1. Behavioral data (events that occur in the system due to students interacting with the system; e.g., time spent logged on) 2. Self-report data (measures of engagement, user experience surveys, the PHQ and GAD7 scores). Participant data will be collected via the TheraGroup systems backend in the form of log data (Behavioral Data) or through Qualtrics (Depression and Anxiety scores, measures of engagement, user experience surveys).

Will recordings be made?

- Yes
- No

If Yes:

- Video Taping
- Audio Taping
- Mandatory Recording
- Voluntary Recording

Is the use of recordings detailed in the consent form?

- Yes
- No

Will recordings be retained?

- Yes
- No

If Yes, how long will records be retained before they are destroyed/erased?

Will any new specimens be collected? (i.e. *blood tissue, etc.*)

- Yes
- No

If Yes, describe what specimens will be used and how they will be obtained:

Does the experiment involve the use of human fluid, tissue and/or blood?

- Yes
- No

Will any invasive or sensitive procedures be done?

Yes No

If Yes, check all that apply:

- Blood Samples
- Physical Measurements (electrodes, etc)
- rDNA
- Stress Exercise
- Urine Samples
- Other, specify: _____

DOCUMENT RETENTION

Federal regulations require that human research documents be retained for a minimum of three years AFTER the completion of the study AND data analysis. Some disciplines or granting agencies require longer retention times.

Length of time retained after completion of study and data analysis:

At least three years

Person responsible for data retention (*If you are a student, please list faculty mentor*) & data storage location:

All data will be kept on a password protected computer in [name] office in [name].

OTHER COMPLIANCE ISSUES

If the study involves the use of **animals, infectious biohazards (e.g. blood), and/or recombinant DNA**, it is required that approval be granted for the use of such through the appropriate compliance committee.

SIGNATURE ASSURANCES

PRINCIPAL INVESTIGATOR

I understand Prairie View A&M University's procedures concerning research involving human subjects and **by initialing** below, I certify:

AL I have read The Belmont Report "Ethical Principles and Guidelines for the Protection of Human Subjects of Research" and subscribe to the principles it contains.

AL I accept responsibility for the scientific and ethical conduct of this research study.

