IRB Member:	 YES	 NO	Date: _____
Social/Behavioral Research Course:	 YES	 NO	Date: _____
IRB accepts Alternative Training:	 YES	 NO	Date: _____
	 YES	 NO	Date: _____

Training Reviewer: _____ Date: _____ 7/9/2024

PROTOCOL APPROVAL

(for office use only)

EXEMPT

Declared by: _____ Date: _____

EXPEDITED

Approved - Reviewer 1: _____ [name]. Date: _____ 10/28/2024

Approved - Reviewer 2: _____ Date: _____

FULL REVIEW

Referred for Full Review: _____ Date: _____

Approved: _____ Date: _____

Date of Full Review (attach minutes): _____

Subject: Opportunity to Participate in a Research Project

Dear PVAMU students,

My name is [name] and I am an Assistant Professor in the Psychology Department at PV. I am emailing you to invite you to be part of a research project about virtual group mental health therapy for Black college students. The purpose of the research is to determine how group telehealth therapy compares to individual telehealth therapy.

If you participate in this project, you will be asked to first complete two mental health assessments. You may then be asked to continue the study and take part in a 12-week virtual therapy program. During this 12-week period you will be asked to complete activities related to the therapy, take mental health assessments, and provide feedback on your experience.

If you participate in this study, you may be eligible to earn up to \$305.00 in the form of an Amazon gift card over approximately 12 weeks of your time. Participation is voluntary, but I hope you will choose to be part of this project. *To participate in the study you must be a Black PVAMU college student of 18 years or older.*

For more information, or to sign up, go to [enter study website here] or contact me at [contact].

Thanks,

[name]

PHQ-9

Over the last 2 weeks, how often have you been bothered by any of the following problems?

Scale: 0 = not at all; 1 = several days; 2 = more than half the days; 3 = nearly every day

1. Little interest or pleasure in doing things
2. Feeling down, depressed, or hopeless
3. Trouble falling or staying asleep, or sleeping too much
4. Feeling tired or having little energy
5. Poor appetite or overeating
6. Feeling bad about yourself or that you are a failure or have let yourself or your family down

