7. Trouble concentrating on things, such as reading the newspaper or watching television
8. Moving or speaking so slowly that other people could have noticed. Or the opposite being so fidgety or restless that you have been moving around a lot more than usual
9. Thoughts that you would be better off dead, or of hurting yourself

GAD-7

Over the last two weeks, how often have you been bothered by the following problems?

Scale: 0 = not at all; 1 = several days; 2 = more than half the days; 3 = nearly every day

1. Feeling nervous, anxious, or on edge
2. Not being able to stop or control worrying
3. Worrying too much about different things
4. Trouble relaxing
5. Being so restless that it is hard to sit still
6. Becoming easily annoyed or irritable
7. Feeling afraid, as if something awful might happen

Engagement

On a scale from 1 to 5 with 1 being not at all to 5 being completely, rate how much the following statement applies to your experience with the telehealth therapy program:

1. I was interested in the therapy
2. I was intrigued when I used the telehealth therapy services
3. I was focused when I used the telehealth therapy services
4. I enjoyed using the telehealth therapy services

5. It was boring to use the telehealth therapy services
6. I felt frustrated using the telehealth therapy services
7. I found the telehealth services confusing
8. I felt unmotivated to use the telehealth services

User Feedback Experience

1. What, if anything, did you enjoy about your experience in using the guided telehealth therapy?
2. What, if anything, could be improved about your experience in using the guided telehealth therapy?
3. Did you feel the psychoeducational content was culturally relevant to you as a Black individual? Please explain

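### The visible procedures state no response to a positive PHQ-9 item 9, either at baseline or during the 12 weeks of therapy

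*Protocol*

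**What the plan says.** The amendment request at the front of the Protocol asks to add a question on suicidality and gives the aim: "If students are suicidal, we want to eliminate them from the study, provide access to resources for them, and alert student counseling services".

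The amended Procedures appear twice, in slightly different wording. Both place the question at entry, before the PHQ-9 and GAD-7, and both give the same consequence of a yes: "If they indicate they have had such thoughts in the prior three weeks, they will be disqualified from the study and a screen will appear". The investigator then brings in Student Counseling Services. The fuller version collects the email address before the question and passes it to that service. The Suicide Assessment section words the question as "In the past few weeks, have you been thinking about killing yourself" and ties the resource list to a yes.

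Students who answer no take both scales. The one stated use of the baseline scores at that step is eligibility: "If they score 5 or above on either test they will be invited to participate in the therapy part of the study". After that, "at week 4, 8 and 12 of therapy, participants will take the GAD-7, PHQ-9, and self-report questionnaires". The SAP uses the same four occasions (baseline and weeks 4, 8 and 12) as its time factor.

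The listed PHQ-9 includes item 9, "Thoughts that you would be better off dead, or of hurting yourself", answered on this scale: "Scale: 0 = not at all; 1 = several days; 2 = more than half the days; 3 = nearly every day". Data Collection says that the scores come "through Qualtrics (Depression and Anxiety scores, measures of engagement, user experience surveys". Therapy itself runs on the TheraGroup platform.

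**The concern.** The study has a resource screen and a referral route, but the visible text connects them to a single yes/no question asked once. It then asks a related and wider question up to four more times, in students recruited because they have symptoms of depression or anxiety, and says nothing about a positive answer. The Risks and Benefits section itself recognises that the surveys and the therapy may worsen existing difficulties.

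What is at stake is participant safety. A student could report thoughts of self-harm on a study form at week 8, and staff who follow the visible procedures would have no instruction to look at the answer, show resources or tell anyone.

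**Working it through.** The plan gives no figure to reproduce, so the check sets the texts side by side.

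**1. Which questions carry a response**

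| Occasion | Question | Who answers | Stated response |
|---|---|---|---|
| Entry | Suicide question, yes/no | All who enter the survey | On yes: disqualification, resource screen, counseling referral |
| Baseline | PHQ-9 item 9, scored 0 to 3 | All who answered no | None stated |
| Week 4 | Item 9 | Participants in therapy | None stated |
| Week 8 | Item 9 | Participants in therapy | None stated |
| Week 12 | Item 9 | Participants in therapy | None stated |

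Administrations of item 9: 1 + 3 = 4, of which 0 have a stated response. One comes before any therapist is assigned and three come after. During the 12 weeks, 0 suicidality questions are linked to an action.

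**2. Whether the entry question already covers item 9**

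- *Content.* The entry question concerns killing oneself. Item 9 also takes in passive thoughts of death and self-harm. A student can truthfully answer no to the first and above zero to the second.
- *Time.* The PHQ-9 looks back 2 weeks. At weeks 4, 8 and 12 its window starts at week 4 − 2 = 2, 8 − 2 = 6 and 12 − 2 = 10 of therapy. All three windows lie after entry, so the entry question cannot speak to them.

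**3. Whether the therapist closes the gap**

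Participants in both arms exchange asynchronous text messages with a therapist, and Risks and Benefits describes those who treat them as qualified. But item 9 is collected in Qualtrics while therapy runs on TheraGroup, and no visible text sends the answer from one to the other. Group members use invented names, and the confidentiality section reserves the link between code and person to the investigator's team.

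**4. Students with no study therapist**

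A student below the cut-off has a PHQ-9 total of at most 4 and a GAD-7 score of at most 4. If item 9 = k, the other eight PHQ-9 items may sum to at most 4 − k:

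- k = 1: at most 3
- k = 2: at most 2
- k = 3: at most 1

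So a positive item 9 below the cut-off is possible, but only in a narrow band of scores. This shows possibility and says nothing about frequency.

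**5. Other visible text that might supply a rule**

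- The Procedures box in the unamended application has no suicide response at all.
- The IRB approval letter requires unanticipated problems and adverse events to be reported to the IRB, but does not tell anyone to read item 9.
- The SAP uses the PHQ-9 only as an outcome.

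**The case against.** Four arguments carry weight.

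*The amendment describes an entry screen, and the procedures deliver one.* A reader might infer that the aim in the amendment request contradicts the procedures because it is not expressly limited to entry. The documents do not support that. The request is to add one question, and removing students from the study is screening language that matches the disqualification step. Applied to weeks 4, 8 and 12, it would mean ending therapy mid-course for a student at risk, which nothing suggests was meant. This objection stands in full: the point is an omission.

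*Silence is not evidence of absence.* A reader might also infer that the survey as built shows no resources after a positive item 9, or that a therapist would learn of risk only if the student raised it. The Qualtrics build is not shown, and nothing says that therapists do not ask about suicidality or cannot see the scores. This stands too. The supportable statement is that no response and no route are stated.

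*Text is missing from view.* Some pages, including the consent pages, were removed, and the risk box in Risks and Benefits breaks off mid-sentence, where mitigation could follow. This stands in part. It lowers certainty. But the amendment names its own changes as the revised procedure and the added question. Both are visible, and the procedure narrative runs from recruitment to week 12 without mentioning item 9.

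*The baseline gap is limited.* Students who report active thoughts have just been screened out and referred, so the uncovered baseline group is those who answer no and still endorse the wider item. This stands, and it moves the weight of the point to risk that emerges during therapy, where a therapist is at least present.

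**Conclusion.** The point holds as an omission in the visible procedures. Resources and referral follow only from a yes at entry. None of the four administrations of item 9 has a stated response, and the three during therapy matter most because no other suicidality question is stated for that period.

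The conclusion assumes that no rule for item 9 stands on a page that cannot be seen; if one does, the defect shrinks to a missing cross-reference. Confidence is therefore medium. The documents do not allow an estimate of how many positive answers to expect, and none is offered. The case for acting rests on the seriousness of a missed report and the low cost of the remedy. A reader might go further and infer bias in the PHQ-9 or GAD-7 comparison, but nothing in the documents supports that.

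**What to change.** In the fuller version of the amended Procedures, which collects the email address first so that it is available for referral, state that:

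1. Any non-zero item 9 at any administration, including in students who then fall below the cut-off, at once shows the resource screen from the Suicide Assessment section and sends a flag to the investigator.
2. The investigator reviews the flag within a stated short time and informs the treating therapist where there is one.
3. The investigator refers to Student Counseling Services by the existing email route at an item 9 threshold agreed with that service and the IRB.
4. A flagged participant stays in therapy unless the clinician decides otherwise, and their PHQ-9 and GAD-7 data stay in the analysis.

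Check that consent covers disclosure to the therapist and to the counseling service. If a rule already exists on an unseen page, a cross-reference in the Procedures is enough. Other schemes would also serve, provided that they name a trigger, a responsible role, a time limit and an action.

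The cost is a short IRB amendment, a consent check and one survey branch on an item already collected electronically. The downside is investigator time to review flags and some false-positive contacts, because item 9 also captures passive thoughts. The agreed threshold keeps referrals in proportion.
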